# 6.3 Secondary Efficacy Endpoints

The *secondary efficacy endpoints* include the change from baseline (PUL 2.0: HOPE-2-OLE Baseline, Cardiac MRI: HOPE-2 Month 12) through Month 60 for the following:

- Upper body functionality using PUL 2.0 assessment (i.e. Upper level PUL:2.0) at Months 12, 24, 36, 48, and 60
- Distal level PUL 2. at Month 12, 24, 36, 48, and 60
- Mid-level (elbow) PUL 2.0 at Month 12, 24, 36, 48, and 60
- LVEF (i.e. Cardiac MRI) at Month<del>,</del> 24, 36, 48, and 60.
- Left Ventricular End Systolic Volume, Indexed (Cardiac MRI) at Month, 24, 36, 48, and 60.
- Left Ventricular End Diastolic Volume, Indexed (Cardiac MRI) at Month, at Month 24, 36, 48, and 60.
- Other cardiac parameters, including but not limited to mass, unindexed volumes, and end diastolic and end systolic wall thickness at 24, 36, 48, and 60.

Observed values and change from baseline will be summarized (n, mean, SD, minimum, and maximum) for all secondary endpoints. Descriptive statistics for the External Comparators, ECP and ECC (section 6.4) will be presented for comparison with endpoints for which data are available.

Further comparisons will be formally made for the 24- and 36-month visits (if available) utilizing real-world evidence from external sources. The data and methods utilized for these comparisons is described in the next section.

# 6.4 External Comparators (Exploratory Efficacy Part 1)

For both the ECP and ECC, propensity score matching will first be attempted to produce an appropriate sample of real-world controls for comparison with the treated subjects from HOPE-2 OLE. If propensity score matching is not appropriate due to small sample size or other limiting factors, then cohort matching will be employed next. In either case, baseline characteristics available in both studies (e.g. baseline LVEF/PUL, age, etc.) will be utilized in the matching algorithm. External Comparator analyses will not be performed or reported if cell sizes are not sufficiently large for statistical analyses after either cohort or propensity score matching is performed. This will be determined separately and independently for the ECP and ECC datasets. If matching is not feasible summary level data may be analyzed.

If propensity score matching is feasible, the following parameterization will be utilized. Greedy nearest-neighbor matching using the logit of the propensity score and an appropriate caliper will be utilized to select matches. Up to 5 matches per treated subject will be used, given available data. Caliper width will be selected such that no treated samples are dropped from the analysis, i.e. at least one control subject will be selected per treated subject. Treated subject records will be sorted in ascending order by propensity score probability.

Baseline characteristics of matched subjects juxtaposed with treated subjects will be reported. In the case of propensity score matching, weighted statistics will be utilized including in analysis and modeling where appropriate.

Indexed volumes will be harmonized between studies: the body-surface area calculation utilized in the HOPE-2 study will be applied to the ECC to recalculate indexed volumes.

The HOPE-2 Month 12 visit will be utilized as the HOPE-2-OLE baseline visit for cardiac MRI parameters, as no cardiac MRI measurements were conducted at the HOPE-2-OLE baseline visit.

The treated and matched controls from the ECP/ECC will be compared using a continuous-time, random slope mixed model with age, baseline, and treatment-by-time interaction. If significant baseline imbalances persist after cohort matching, a baseline-by-treatment interaction term will be included in the model. Slope differences between groups will be presented along with the estimated treatment difference at 24 months (for ECC) and 36 months (for ECP) with corresponding 95% confidence intervals and associated two-sided p-values. The Kenward Roger approximation will be utilized to calculate denominator degrees of freedom. A percentile rank transformation will be applied to the change from baseline and baseline values in case model assumptions are violated.

Furthermore, a global statistical test (GST) may be employed to explore the totality of evidence across multiple cardiac endpoints, such as Left Ventricular Ejection Fraction, Indexed Left Ventricular End Systolic Volume, Indexed Left Ventricular End Diastolic Volume, and other cardiac MRI measures collected in HOPE-2 OLE and in the ECC. The GST will be constructed as follows:

• For each distinct parameter in the GST, calculate the standardized change from baseline as follows:

$$chg'_{i,t,p} = \frac{x_{i,t,p} - \mu_p}{\sigma^{pooled}_{t,p}}$$

where *i*, *t*, *p* represent the *i*th subject, the timepoint (visit) *t*, and the *p*th parameter in the GST, *x* represents the raw score (analysis value),  $\mu$  represents the mean baseline value for parameter,  $\sigma^{pooled}$  is the standard deviation of  $x_{t,p}$  pooled between control and treatment arms, and *chg'* is the standardized change from baseline.

Then, by subject and visit, calculate the mean standardized change from baseline as:

$$chg_{i,t}^{gst} = \frac{1}{n} \sum_{p=1}^{n} chg_{i,t,p}',$$

where  $chg^{gst}$  represents the change from baseline score of the GST.

Baseline values will be calculated in the same manner using baseline analysis values for each parameter and only with the baseline visit. If any of the baseline components do not have a calculable baseline value, baseline will be calculated from the available measures. Scales will be directionally aligned in determination of the final score.

For percentile rank transformed variables, potentially (Left Ventricular Ejection Fraction, Indexed Left Ventricular End Systolic Volume, Indexed Left Ventricular End Diastolic Volume, Heart Chamber Volume End Diastolic Volume, and Heart Chamber Volume End Systolic Volume), the GST will be calculated using the average percentile rank instead of the process described above. Otherwise, all other rules for the construction of the GST will apply.

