### 6.5 Sensitivity Analyses

Sensitivity analyses will be performed to test the robustness of the External Comparator analysis results for LVEF. Analyses exploring the hyperparameters of the propensity score matching algorithm will be presented. Random ordering will be employed to test the sensitivity of the match algorithm to sort order. Furthermore, results from an optimal propensity matching algorithm with appropriate k and caliper width will be presented.

The following outcome analyses will be performed using the matched set from the primary analysis:

- A Wilcoxon rank test comparing the change from baseline between the two groups,
- Change from baseline to Month 24 using an ANCOVA model with treatment as a factor and baseline and age as potential covariates.

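### External PUL comparison (SAP 6.4): the baseline-by-treatment term meant to correct residual imbalance leaves the bias in the slope and 36-month differences

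*SAP*

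**What the plan says.** SAP 6.4 first tries propensity score matching of external controls, then cohort matching if that is unsuitable. Baseline PUL and age are among the suggested matching variables. Up to five controls are taken per treated subject, and "Caliper width will be selected such that no treated samples are dropped from the analysis". After propensity matching, "weighted statistics will be utilized including in analysis and modeling where appropriate". For either method, "Baseline characteristics of matched subjects juxtaposed with treated subjects will be reported".

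The outcome model is a continuous-time "random slope mixed model with age, baseline, and treatment-by-time interaction". It yields a slope difference and, for ECP, a treatment difference at 36 months, each with a 95% confidence interval and a two-sided p-value. The only model-based response to remaining imbalance is: "If significant baseline imbalances persist after cohort matching, a baseline-by-treatment interaction term will be included in the model".

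SAP 6.3 introduces the comparison with the words "Further comparisons will be formally made for the 24- and 36-month visits (if available) utilizing real-world evidence from external sources". SAP 6.5 gives robustness checks for one outcome: "Sensitivity analyses will be performed to test the robustness of the External Comparator analysis results for LVEF". Among them is "Change from baseline to Month 24 using an ANCOVA model with treatment as a factor and baseline and age as potential covariates".

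**The concern.** The quantities reported are a difference in slope and a difference at a late time point. Confounding of a slope comes from covariates that predict the rate of change. Removing it needs those covariates crossed with time. On the natural reading of SAP 6.4, only treatment is crossed with time. Age and baseline shift the level of the outcome, and the conditional baseline-by-treatment term lets that shift differ by group. None of them lets the rate of decline depend on baseline or age.

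The conditional sentence exists only for the case where imbalance persists, and in that case it does not correct the estimates reported. A reader could see an imbalance in the baseline table, see that a term was added, and wrongly take the PUL slope as adjusted.

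Related gaps:

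- The model is not fully written. No treatment main effect is listed, and the phrase could be stretched to mean that all three terms are crossed with time.
- The trigger, significant imbalance, has no test or threshold.
- The propensity branch has no covariate-by-time term either, and its caliper rule can keep poor matches.
- The added term does nothing for age, and it makes the 36-month difference depend on a baseline value the SAP does not name.
- No check equivalent to the LVEF ANCOVA is written for PUL.

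**Working it through.** The plan states no bias or power figure for this comparison, so there is none to reproduce.

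**Inputs from the documents.** 13 treated subjects (SAP 3.1 and 4.1); up to five controls each (SAP 6.4); PUL every three months in treated subjects (Protocol 12.1); two-sided p-values (SAP 6.4).

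**Assumed inputs.** 39 controls; residual imbalance Δ of 0.25 to 0.75 SD; dependence of decline on baseline γ of 0.3 to 0.6 points/year per SD; intercept SD 1; residual SD 1.5; slope SD 0.5, 1.0 or 1.5. The true treatment effect is zero throughout.

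**Step 1: algebra.** Let subject i change at rate β + γ·bᵢ + uᵢ, where bᵢ is baseline in SD units. With common visits and a treatment main effect in the model, the slope difference is the difference in mean subject slopes. Its expectation is γ·Δ, and terms constant over time do not enter it.

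- Low corner: 0.3 × 0.25 = 0.075 points/year.
- Middle: 0.6 × 0.5 = 0.30 points/year.
- High corner: 0.6 × 0.75 = 0.45 points/year.

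Without the main effect, the fitted group lines are forced together at time zero. The bias is then smaller but does not vanish.

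**Step 2: exact generalised least squares, Δ = 0.5 SD, γ = 0.6.** Change from baseline is the outcome, with no time-zero record. Entries are slope bias in points/year for slope SD 0.5 / 1.0 / 1.5, with rejection at nominal 5% in brackets where computed.

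| Model | Six half-yearly visits, 40% missing | Treated quarterly, controls yearly, 10% missing |
|---|---|---|
| Terms as listed | 0.15 / 0.20 / 0.23 (11.0 / 9.7 / 8.3%) | 0.19 / 0.24 / 0.27 (16.8 / 12.7 / 9.8%) |
| As listed + baseline-by-treatment | 0.16 / 0.21 / 0.24 | 0.23 / 0.27 / 0.29 |
| With treatment main effect | 0.27 / 0.28 / 0.28 (15.9 / 11.6 / 9.0%) | 0.31 throughout (24.5 / 15.3 / 10.7%) |
| Main effect + baseline-by-treatment | unchanged | 0.31 |
| With baseline-by-time and age-by-time | 0.000 (5.0%) | 0.000 (5.0%) |

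For the terms as listed, the 36-month difference is three times the slope: 3 × 0.15 = 0.45 to 3 × 0.27 = 0.81 points. Across both model forms the range is 0.45 to 0.82.

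**Step 3: range over the assumed grid.** The false slope is 0.03 to 0.41 points/year for the terms as listed and 0.06 to 0.46 with a main effect. Rejection is 5.4 to 7.4% at the low corner, effectively nominal. It reaches 17 to 39% only at 0.75 SD, 0.6 and the smallest slope SD. Baseline-by-treatment never reduces the mean slope bias by more than 0.001.

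**Step 4: REML fits** (400 simulated trials, slope SD 0.5, 40% missing).

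| Model | Slope bias | Rejection |
|---|---|---|
| As listed | 0.199 | 9.2% |
| + baseline-by-treatment | 0.203 | 9.2% |
| With main effect | 0.322 | 13.0% |
| Main effect + baseline-by-treatment | 0.323 | 13.0% |
| Time interactions, without / with main effect | 0.023 / 0.003 | 3.2 / 3.2% |

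**Step 5: separate derivation on a raw scale, with a main effect.** Imbalances of +2 PUL points and −1 year, with dependences of 0.1 and −0.1 points/year per unit, give 2 × 0.1 + (−1) × (−0.1) = 0.30 points/year. REML with common visits estimated 0.298 both with and without baseline-by-treatment, and −0.007 (Monte Carlo SE 0.050) with the time interactions. Time-constant terms shrink the 36-month bias somewhat, but about 56 to 95% of it remains.

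**Step 6: can imbalance survive the matching rule?** This applies to the propensity branch only: greedy 1:5 matching, ascending order, caliper widened until all 13 treated subjects match, 600 runs. The table gives the share of runs with weighted baseline imbalance above 0.25 SD.

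| Control pool | Pre-match shift 0.25 SD | 0.5 SD | 0.75 SD |
|---|---|---|---|
| 40 | 13% | 32% | 67% |
| 80 | 3% | 14% | 31% |
| 150 | 4% | 4% | 14% |

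**Step 7: the trigger.** If significant means a 5% two-sample t-test, the noncentrality for a 0.5 SD imbalance against m controls is 0.5 × √(13m/(13 + m)). For m = 13, 39 and 65 this is 1.27, 1.56 and 1.65, so the imbalance is flagged 23%, 33% and 37% of the time.

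**The case against.** The strongest reply is that the wording is shorthand. If the time interaction is meant to cover age and baseline as well as treatment, the model already contains the correction and the bias disappears. That is true of that reading, but the text does not say it, and the model needs writing out either way.

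Second, imbalance is handled first by matching on baseline and age. The baseline-by-treatment sentence applies only after cohort matching, which is itself the fallback, and the comparison is dropped if cells are too small. The residual-imbalance percentages above come from the propensity branch. No estimate exists for cohort matching, and the worst cell uses a small pool that might itself lead the sponsor away from propensity matching. This limits how often the problem would arise. It does not rescue a rule that fails in the one case it was written for, and the propensity branch has no covariate-by-time term either.

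Third, the section is exploratory, p-values are nominal, the primary Month 12 summary is untouched, and every magnitude input is assumed. All of this stands. The figures show that the bias is possible and what size it could take, not that it is likely.

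**Conclusion.** The concern holds. On the natural reading of SAP 6.4, neither the listed covariates nor the baseline-by-treatment term removes imbalance bias from the ECP slope or 36-month difference, with or without a treatment main effect. Bias requires both residual imbalance and a rate of decline that depends on baseline or age. If either is absent, it is zero.

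Under a moderate assumed setting (0.5 SD, 0.6 points/year per SD), the false 36-month PUL difference is 0.45 to 0.82 points and nominal 5% error becomes 8 to 25%. At the low end of the assumed range, error is close to nominal. This should be changed before the comparison is run, although it does not affect the primary analysis. Confidence is medium because the documents supply none of the size inputs.

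**What to change.** **ECP.**

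- Write the model out in full, stating whether a treatment main effect is included.
- Replace the conditional baseline-by-treatment sentence with prespecified, centred baseline-by-time and age-by-time terms, in both the propensity and cohort branches and regardless of any imbalance test. This works with or without the main effect.
- Judge post-match balance by standardised mean differences, with the threshold stated in advance.

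**Cardiac comparator (ECC).** Do not carry over a treatment main effect as a requirement. OLE cardiac MRI starts at Month 24 (Protocol 12.2). Under assumed inputs (slope SD 1, visit windows ±21 days), a main effect raises the slope standard error from 0.45 to 27 with Month 24 alone, and from 0.38 to 0.75 with Months 24 and 36. Keep the Month 24 ANCOVA in SAP 6.5 as the check, with baseline and age as fixed rather than potential covariates.

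**Cost.** SAP wording only, with no new data. The ECP model gains two fixed-effect parameters. At fixed covariance, the slope standard error rises by about 2 to 7% without a treatment main effect and 3 to 10% with one.

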#### 13.2. Sample Size

Up to 16 subjects who were enrolled in the HOPE-2 trial and completed the 12-month follow-up period will be enrolled in this trial.

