### 3.1 Sample Size

Thirteen subjects who were enrolled in and completed the 12-month randomized period in the HOPE-2 trial will be enrolled in this trial.

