### 4.1 Study Phases

There will be three phases of the overall HOPE-2 study identified in the analysis, defined as follows:

- 1. **Main Phase**: The double-blind HOPE-2 study which followed subjects from baseline through 12 months of follow-up. Twenty subjects completed this study. Of these 20 subjects, 13 enrolled in the HOPE-2-OLE study.
- 2. **Gap Phase:** The gap period, approximately 1 year for each of the 13 subjects, between the end of HOPE-2 12-month visit and the Baseline visit of the OLE Phase.
- **3. OLE Phase:** The unblinded open-label extension study (HOPE-2-OLE) described in this SAP and cited protocol, consisting of 13 subjects all treated with deramiocel for up to 57-months.

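### SAP 6.4 acts on baseline imbalance against external controls only if it is *significant* (undefined) and only after cohort matching; the preferred propensity route has no balance rule

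*SAP*

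**What the plan says.** SAP 6.4 builds external control groups for PUL 2.0 (ECP) and cardiac MRI (ECC). Propensity score matching is tried first. Cohort matching is the fallback: "If propensity score matching is not appropriate due to small sample size or other limiting factors, then cohort matching will be employed next".

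On the propensity route the ratio is bounded above, "Up to 5 matches per treated subject will be used, given available data", and below: the caliper is chosen so that "at least one control subject will be selected per treated subject" and no treated subject is lost. No ratio is given for cohort matching.

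Two sentences deal with balance afterwards. One is descriptive: "Baseline characteristics of matched subjects juxtaposed with treated subjects will be reported". The other is the only one that changes the analysis because of imbalance: "If significant baseline imbalances persist after cohort matching, a baseline-by-treatment interaction term will be included in the model".

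The outcome model is a continuous-time random-slope mixed model. Its listed terms are age, baseline and treatment-by-time. It yields a slope difference and a treatment difference at 24 months (ECC) or 36 months (ECP), with confidence intervals and p-values. SAP 6.5 varies the matching algorithm for LVEF but sets no balance criterion.

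**The concern.** Whether matched external subjects are comparable is a question about the size of the remaining difference. A significance trigger answers another question, namely whether the sample is large enough to show a difference. With 13 treated subjects the two can diverge widely. Reading *significant* as *substantial* does not help, since with no limit stated the decision falls to judgement at analysis.

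The rule is also attached to the fallback route. On the preferred route the caliper has to widen until the hardest-to-match treated subject has a control, so it cannot be relied on to exclude poor matches. A balance criterion would normally take over that job, and there is none.

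SAP 6.3 says the 24- and 36-month comparisons are formally made, and they are the only modelled between-group comparison for this single-arm trial. Imbalance in a prognostic variable can pass directly into the reported slope difference.

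**Working it through.** The plan gives no figure for the sensitivity of this check, so there is none to reproduce. The calculation below is conditional on the stated assumptions.

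**Inputs from the documents.** There are 13 treated subjects: SAP 3.1, "Thirteen subjects who were enrolled in and completed the 12-month randomized period in the HOPE-2 trial will be enrolled in this trial", and SAP 4.1, "Of these 20 subjects, 13 enrolled in the HOPE-2-OLE study". Protocol 13.2 allows more: "Up to 16 subjects who were enrolled in the HOPE-2 trial and completed the 12-month follow-up period will be enrolled in this trial". Ratios of 1:1 to 1:5 come from the propensity route and are borrowed here; 1:10 is added because the cohort ratio is unstated.

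**Assumptions.** Two-sided 5% two-sample t-test, one covariate, true imbalance d = 0.5 SD.

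**Formulas.** With n1 = 13 treated and n2 controls:
- standard error in SD units: s = √(1/n1 + 1/n2)
- noncentrality: δ = d/s
- critical value: c = t(0.975, n1 + n2 − 2)
- smallest observed difference that reaches significance: c × s
- chance of no action: P(−c < T < c), with T noncentral t with parameter δ

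| Ratio | n2 | s | δ | c | c × s (SD) | No action |
|---|---|---|---|---|---|---|
| 1:1 | 13 | 0.392 | 1.275 | 2.064 | 0.81 | 76.8% |
| 1:2 | 26 | 0.340 | 1.472 | 2.026 | 0.69 | 70.0% |
| 1:3 | 39 | 0.320 | 1.561 | 2.009 | 0.64 | 66.6% |
| 1:5 | 65 | 0.304 | 1.646 | 1.992 | 0.61 | 63.1% |
| 1:10 | 130 | 0.291 | 1.719 | 1.977 | 0.58 | 60.0% |

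At 1:100 the figure is still 56.6%, because the 13 treated subjects set the floor. The same holds for observed differences: an observed difference of 0.5 SD has t = 1.275, p = 0.21 at 1:1 and t = 1.646, p = 0.10 at 1:5.

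**Sensitivity to the assumptions** (1:1 to 1:5):
- alpha 0.10: 65.6% to 50.5%
- alpha 0.20: 50.6% to 35.9%
- 10 treated subjects with data: 81.5% to 70.5%
- 16 treated subjects: 72.2% to 56.1%
- three independent covariates, each out by 0.5 SD, none triggering: 0.768³ = 45% to 0.631³ = 25%

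**Do the age and baseline terms already deal with it?** Suppose the yearly slope changes by 0.5 units per SD of a covariate (an assumption), and the groups differ by 0.5 SD. With no treatment effect, the expected false slope difference is 0.5 × 0.5 = 0.25 units per year. A main effect shifts a subject's whole trajectory by a constant and does not explain why some subjects decline faster. Illustrative random-slope simulations with these values and the covariate as a main effect only left about 0.19 to 0.27 units per year. Adding covariate-by-time reduced it to about 0.02 or to nothing beyond simulation error. The SAP lists no age-by-time or baseline-by-time term, and matching variables other than age and baseline have no term.

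**The case against.** The strongest reply is that the SAP does not declare the groups balanced. Age and baseline are in the model whatever the trigger shows, so a missed trigger omits only a baseline-by-treatment term. Matched baselines are reported side by side, weighting is used after propensity matching, the analysis is withheld if cell sizes are too small, and SAP 6.5 tests sort order and an optimal match for LVEF. The section is headed exploratory. All of this is true. It rules out saying that the plan treats non-significance as proof of balance. It does not supply a balance criterion, and the main effects do not protect a slope comparison.

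Three stronger readings are tempting, and the documents do not support them:
- A reader might take 63–77% as a property of the SAP. It is not: test, alpha and imbalance size are assumed, the ratios come from the other matching route, and checking several covariates raises the chance that one triggers.
- A reader might infer that imbalance after propensity matching is missed 100% of the time. No rule applies there, so there is no miss rate to quote.
- A reader might infer that the poorest matches get the least scrutiny because fewer controls give less power. Fewer controls need not be worse ones: nearest-neighbour 1:1 keeps the closest control, and adding more brings in more distant ones.

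A fair point against any fixed limit is that small samples cross it by chance. For two unmatched samples with no true difference, 0.25/0.392 = 0.64 and 0.25/0.304 = 0.82. On a normal approximation, a limit of 0.25 would then be exceeded about 52% of the time at 1:1 and 41% at 1:5 for each covariate. Successful matching would lower this. The consequence of crossing should therefore be adjustment and labelling, not failure of the comparison.

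**Conclusion.** The point holds in this form: the only action on residual imbalance rests on an undefined word, applies only on the fallback route, and leaves the preferred route without a rule. If the word means p<0.05 on a two-sided t-test, a true 0.5-SD imbalance in one covariate would prompt no action in roughly 60% to 77% of cases over ratios from 1:10 to 1:1. That range falls with a looser alpha and rises if fewer than 13 treated subjects have data. If the word means *substantial*, no rate can be given and the decision is unspecified. How much bias follows depends on how strongly the covariate predicts decline, which the documents do not say; the 0.25 units per year above is illustrative. This should be changed, but it bears on exploratory comparisons and not on the primary endpoint summary.

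**What to change.** Replace the trigger sentence in SAP 6.4 with a rule for both routes, for example:

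*After propensity score or cohort matching, balance on each matching variable is judged by its standardized mean difference (weighted where weights are used), not by a p-value. The limit is 0.25. If a variable exceeds it, matching is refined without reference to outcomes. If it still exceeds the limit, that variable and its interaction with time are added to the outcome model, and the comparison is reported as not balanced on that variable.*

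The value 0.25 is a proposal. What matters is that a limit, and the list of matching variables, are fixed before the external-comparator outcomes are analysed. The trial is open-label and Protocol 4.4 already describes interim results, so the SAP should also say that matching decisions are made without using outcome data.

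The cost is SAP wording plus one column in a baseline table that is already planned. The downside is that, with 13 treated subjects, the limit will often be crossed by chance. Some comparisons will then carry an unbalanced label or extra model terms, and at 1:1 those terms must be estimated from 26 subjects.
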